3.3 Discontinuation Criteria

If a patient decides to discontinue protocol treatment or progression of disease is detected, follow up and data collection will continue as specified in the protocol.

3.4 Criteria for Termination of Protocol

The trial will be terminated if there is a greater than 12% clinically significant, treatment-Phase II – Enzalutamide and Radiation

related grade 3 or higher toxicity. The 12% clinically significant, treatment-related acute grade 3 or higher toxicity rate is acceptable as prior studies have demonstrated a 12% acute grade 3 GU and GI toxicity. The use of a urinary catheter or bladder irrigation within 14 days after brachytherapy will not be considered grade 2 toxicity as this may be a standard procedure after brachytherapy. The trial will not be terminated for non-related or non-clinically significant toxicities.

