5.1.1 Anti-Androgen Therapy: Enzalutamide

Timing: Enzalutamide therapy will begin within 0-7 days (can begin before or same day as, or after) of the date of the first LHRH agonist administration and continue for a total duration of 24 months. The total duration of administered anti-androgen therapy must be documented and submitted.

Description: Enzalutamide is a nonsteroidal androgen receptor antagonist developed by the pharmaceutical company Medivation/Astellas. The chemical name is 4-(3-(4-Cyano-3-(trifluoromethyl)phenyl)-5,5-dimethyl-4-oxo-2-thioxoimidazolidin-1-yl)-2-fluoro-N-methylbenzamide. Enzalutamide has approximately 9-fold greater binding affinity to the androgen receptor compared to the antiandrogen bicalutamide. As opposed to

Version date: 09-05-2017

Protocol CC#: 15558

bicalutamide, enzalutamide does not promote translocation of the androgen receptor to the nucleus and in addition prevents binding of the androgen receptor to DNA and to coactivator proteins. In two clinical trials in patients with metastatic castration-resistant prostate cancer pre- and post-docetaxel (PREVAIL and AFFIRM, respectively), enzalutamide demonstrated improvements in overall survival and was well-tolerated.

Supply: From Medivation/Astellas through NCCN's vendor CRMG

Storage: Enzalutamide should be stored in a dry place at room temperature between 68°-77°F.

Administration: Enzalutamide is administered orally at a dose of 160 mg (for 40 mg capsules) per day. Enzalutamide can be taken with or without food. Swallow capsules whole. Do not chew, dissolve, or open the capsules.

Administration will be suspended only if there is an apparent or suspected reaction to the drug. During RT interruptions, enzalutamide will be continued. Any treatment interruptions or failure of the patient to comply with the prescribed medication schedule must be documented.

Toxicity: Consult the package insert for comprehensive toxicity information (Table 5).

Table 5: Adverse Reactions

| | ENZALUTAMIDE (N=800) | | PLACEBO (N=399) | |
|--|----------------------|---------------------|---------------------|---------------------|
| General Disorders | Grade 1-4(%) | Grade 3-4(%) | Grade 1-4(%) | Grade 3-4(%) |
| Asthenic Conditions | 50.6 | 9.0 | 44.4 | 9.3 |
| Peripheral Edema | 15.4 | 1.0 | 13.3 | 0.8 |
| Musculoskeletal and Connective Tissue Disorders | | | | |
| Back Pain | 26.4 | 5.3 | 24.3 | 4.0 |
| Arthralgia | 20.5 | 2.5 | 17.3 | 1.8 |

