9.2 Determination of Sample Size and Accrual Rate

9.2.1 Sample Size and Power Estimate

Sample size is determined based on the primary objective of the PSA-CR. This is a single arm study with the primary endpoint evaluating the proportion of patients experiencing a PSA-CR. From historical controls (RTOG 9413 and MSKCC as mentioned in background information), we expect 70% of patients to experience a PSA-CR. With addition of enzalutamide, at least 85% of patients are expected to attain a PSA-CR. With 53 patients (10% dropout rate), we would have 80% power to detect thus improvement at significance level of 0.05 based on directional binomial test.

As we expect the combined enzalutamide and leuprolide regimen does not significantly increase grade 3 or greater acute or late toxicity for treatment of intermediate- to high-risk prostate cancer and the usual rate of 3 or greater toxicity is approximately 12%. If the true grade 3 or greater acute or late toxicity rate is 12%, with 47 patients we will have 80% confidence in the toxicity rate estimate with precision of 4.7% (i.e. a confidence interval width of 9.4%).

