9.3 Interim Analyses and Stopping Rules

Continuous safety monitoring will be performed throughout the trial. The trial will be terminated if there is a greater 12% acute grade 3 toxicity. This rate is acceptable as prior studies have demonstrated 8-15% acute grade 3 GU and GI toxicity when irradiating the pelvis using standard fractionated technique to 45 Gy in 1.8 Gy fractions followed by brachytherapy boost

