9.4.2 Primary Analysis (or Analysis of Primary Endpoints)

Point estimates and 95% confidence intervals of PSA-CR will be obtained. The PSA-CR will be compared with the historical rate by binomial test.

Toxicity will be assessed by CTCAE v4.0. Point estimation and its 95% confidence interval will be calculated for the rate of acute Grade 3 or greater toxicity within 24 months of completing treatment with radiotherapy. Furthermore, one sample proportion test will be used to test hypothesis that the addition of enzalutamide to leuprolide and radiation therapy does not significantly increase acute or late toxicity.

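### The 12% toxicity reference is sourced as acute GU and GI toxicity only, but 9.2.1 and 9.4.2 set it against grade 3 or greater acute or late toxicity of any organ system

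*Combined protocol and SAP*

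**What the plan says.** The figure is sourced in two places, both times as acute toxicity of two organ systems. Section 3.4 justifies the termination threshold by saying that "prior studies have demonstrated a 12% acute grade 3 GU and GI toxicity". Section 9.3 justifies the same threshold with a range: "prior studies have demonstrated 8-15% acute grade 3 GU and GI toxicity when irradiating the pelvis", the setting being conventional fractionation to 45 Gy followed by a brachytherapy boost.

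The toxicity objective uses the figure without those limits:

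- Section 2.4.1 makes acute toxicity (up to 90 days after radiotherapy) and late toxicity (from day 91) the first primary endpoint, graded by CTCAE v4.0, with no restriction by organ system or attribution.
- Section 9.2.1 states that "the usual rate of 3 or greater toxicity is approximately 12" per cent, then bases its precision statement on the wider event: "If the true grade 3 or greater acute or late toxicity rate is 12%, with 47 patients".
- Section 9.4.2 plans a one-sample proportion test of the hypothesis that the "addition of enzalutamide to leuprolide and radiation therapy does not significantly increase acute or late toxicity". It gives no null value, significance level or sidedness. It also describes as acute a rate counted over 24 months after radiotherapy, which conflicts with the 90-day limit in 2.4.1.

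The termination rule in 3.4 is limited to clinically significant, treatment-related events. The restatement in 9.3 drops that limit and refers to acute grade 3 toxicity.

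**The concern.** A one-sample comparison is interpretable only if the historical rate and the observed rate count the same events. Here they differ in organ system (GU and GI against any) and in time window (acute against acute or late). Both differences can only add events to the observed side, so the comparison leans towards finding an increase.

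Safety and feasibility form the first primary objective, there is no control arm, and 12% is the only reference rate offered for it. Patients also receive 24 months of leuprolide, for which 5.1.1 lists many effects outside the GU and GI systems. Table 5 shows that severe non-GU/GI events occur without enzalutamide. In the row "Asthenic Conditions | 50.6 | 9.0 | 44.4 | 9.3" the second and fourth figures are the grade 3-4 percentages on enzalutamide and on placebo. A regimen with exactly the historical acute GU/GI toxicity could therefore be reported as more toxic than its reference because of events the reference never counted.

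**Working it through.** **The plan's own figure.** Section 9.2.1 claims precision of 4.7% at 80% confidence, with 47 patients and a true rate of 12%. The standard error is √(0.12 × 0.88 / 47) = 4.74%, and the two-sided 80% half-width is 1.2816 × 4.74% = 6.07%. The stated 4.7% is therefore one standard error, or about 68% confidence. This is a separate slip in the same paragraph, and nothing below depends on it.

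**Inputs for the test.**

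- Reference rate p0 = 12%. It is inferred as the null because 9.2.1 offers no other rate.
- n = 47 (9.2.1) and n = 53 (planned enrolment, since 9.4.1 analyses all patients).
- Exact binomial test, one-sided at 5%. This is an assumption.
- Acute grade 3+ GU/GI rate unchanged at 12%, so that enzalutamide has no effect on it.
- A share b of patients with some other grade 3+ event, independent of the GU/GI events and not caused by enzalutamide. The documents give no such rate for this population. I take b = 3%, 5% and 9%. The first two are assumed. The last is the Table 5 asthenia figure, an upper value because those trials enrolled patients with metastatic castration-resistant disease.

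**Rejection rule.** Take the smallest r with P(X ≥ r | n, 0.12) ≤ 0.05.

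- n = 47: P(X ≥ 9) = 10.4% and P(X ≥ 10) = 4.9%, so reject at 10 or more (10/47 = 21.3%).
- n = 53: P(X ≥ 10) = 9.7% and P(X ≥ 11) = 4.8%, so reject at 11 or more (11/53 = 20.8%).

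**Counted rate and chance of declaring an increase.** The counted rate is q = 1 − 0.88 × (1 − b).

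| b | q | n = 47 | n = 53 |
|---|---|---|---|
| 0 | 12.0% | 4.9% | 4.8% |
| 3% | 1 − 0.88 × 0.97 = 14.6% | 14.1% | 14.4% |
| 5% | 1 − 0.88 × 0.95 = 16.4% | 23.3% | 24.4% |
| 9% | 1 − 0.88 × 0.91 = 19.9% | 46.5% | 49.4% |

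**Sensitivity to the GU/GI rate.** Section 9.3 allows 8-15%. With 47 patients and a true GU/GI rate of 8%, the three values of b give 2.6%, 6.5% and 22.6%. With a true rate of 15% they give 30.5%, 41.9% and 64.5%, but at 15% the test already rejects 15.8% of the time with b = 0. The mismatch raises the chance in every case. Its absolute size depends on rates that the documents do not fix.

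**The case against.** Several points on the other side stand.

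- **The termination rule has a filter.** A reader might infer that background events would stop the trial. Section 3.4 excludes unrelated and clinically insignificant toxicity, so the documents do not support that for 3.4. Leuprolide- or radiation-related events outside GU/GI could still count, and 9.3 omits the filter. The point belongs mainly at 9.2.1 and 9.4.2.
- **The null is inferred.** Section 9.2.1 uses 12% for a precision statement, and 9.4.2 names no null. The 12% might also have a broader source, because 9.2.1 describes it without an organ limit. None is cited, and both places that give an origin say acute GU/GI.
- **The background rates are soft.** The 3% scenario gives 14.6%, which lies inside the 8-15% range in 9.3. One could also add grade 3-4 hypertension from Table 5 to the 9% and reach 1 − 0.88 × 0.91 × 0.979 = 21.6%, with a 58% chance of rejection. That uses the enzalutamide-arm rate (2.1%, against 1.3% on placebo), so part of it may be a real drug effect. I do not rely on it.
- **Systemic events belong in the safety question.** Hypertension and falls were more frequent on enzalutamide than on placebo in Table 5. Counting them is right, and only the comparator is mismatched.
- **The GU/GI signal is not lost.** Section 7.2 summarises the maximum severity of each adverse event, and 7.4 records grade 3+ events with attribution, so GU/GI events can be separated at analysis.

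These points limit the size and reach of the problem. None supplies a reference rate that covers the events to be counted.

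**Conclusion.** The mismatch stands on the text. In 9.2.1 and 9.4.2, read with the endpoint in 2.4.1, the only reference rate counts fewer kinds of event, over a shorter period, than the rate it is to judge. The comparison is biased towards finding an increase.

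Under an inferred 12% null, an assumed exact one-sided 5% test, acute GU/GI toxicity unchanged at 12% and an assumed 3-9% of patients with other independent grade 3+ events, the false-increase probability is about 14% to 46.5% with 47 patients and 14% to 49% with 53, against about 5% nominal. The upper end borrows from a metastatic population. Late events are not modelled separately, and any beyond the assumed share would add to the counted rate.

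The documents do not support saying that enzalutamide will be wrongly judged toxic, or that background events will trigger termination under 3.4. They show that a finding of increased toxicity against 12% could not be attributed to enzalutamide.

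**What to change.** In 9.2.1 and 9.4.2, state the null value, level and sidedness. Compare with 12% only the matched event: the proportion of patients with acute (up to 90 days after radiotherapy, as in 2.4.1) grade 3 or higher GU or GI toxicity. Remove the 24-month window from what 9.4.2 calls acute.

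Keep late toxicity and all other grade 3+ toxicity in the primary safety endpoint. Report them as separate estimates with 95% confidence intervals, and do not test them against 12% unless a benchmark covering those events is cited.

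For 3.4 and 9.3, reconcile the two wordings of the termination rule (attribution, grade, time window, organ system) with each other and with the source of the 12%. Which events count towards stopping is not for this point to settle.

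The cost is wording and one more table, since grade 3+ events are already recorded with CTCAE grade and attribution. The downside is that systemic and late toxicity are then judged from estimates rather than a test. The matched test is also modest in power: with 47 patients it rejects 12% with probability 47% if the true acute GU/GI rate is 20%, and 77% if it is 25%. A non-significant result should therefore not be read as showing no increase.

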3.5 Duration of Therapy

In the absence of treatment delays due to adverse events, treatment may continue for up to 24 months or until:

- Disease progression
- Inter-current illness that prevents further administration of treatment
- Unacceptable adverse event(s)
- Patient decides to withdraw from the study
- Significant patient non-compliance with the protocol
- General or specific changes in the patient's condition render the patient unacceptable for further treatment in the judgment of the investigator.

3.6 Duration of Follow up

After completion of radiation treatment, patients will be followed at 6 weeks, month 3-4, month 6, month 12, month 18, month 24, and at 36 months per standard of care. Patients removed from study for unacceptable treatment related adverse event(s) will be followed until resolution or stabilization of all treatment related adverse events to Grade 2 or lower.

3.7 Study Timeline

3.7.1 Primary Completion

Study accrual is to be completed by 24 months

3.7.2 Study Completion

Study completion is projected approximately 60 months from the time the study is open to accrual.

4 Radiation Therapy

Radiation therapy should begin approximately 8 weeks (+/- 1 week) after the date of the first LHRH agonist/antagonist injection of hormone therapy is given.

4.1 Two Stage Radiation Plan

4.1.1 Phase 1: Whole pelvis including prostate and seminal vesicles.

IMRT will be utilized for treatment delivery.

Prescription Dose (See Table 1):

45 Gy to cover 98% of PTV

- Minimum dose within PTV – 95% of prescribed dose and for a volume

- that is 0.03 cc.
- Maximum dose within the PTV – 107% of prescribed dose and for a volume that is 0.03 cc.

Table 1: IMRT Dose Objectives for Phase 1 – Pelvic and Prostate Radiation

| PTV Dose (encompassing 98% of PTV) | Minimum PTV dose for a point with a volume of 0.03 cc | Maximum PTV dose to a volume of 0.03 cc of PTV ¹ (Per Protocol) | Maximum PTV dose to a volume of 0.03 cc of PTV ¹ (Variation Acceptable) | Maximum PTV dose to a volume of 0.03 cc of PTV ¹ (Deviation unacceptable) |
|---------------------------------------|---|---|---|---|
| 45 Gy | 42.8 Gy | 48.2 Gy | >48.2 – 49.5 Gy | >49.5 Gy |

4.1.2. Phase 2: Reduced volume to boost prostate and seminal vesicles

Acceptable Treatment Modalities: IMRT, Stereotactic body radiotherapy, permanent prostate implant (PPI) brachytherapy or high-dose rate (HDR) brachytherapy

Table 2: Treatment Modalities and Prescription Dose for Phase 2

| Acceptable Treatment Modalities | Prescription Dose |
|---------------------------------------|--|
| Intensity-Modulated Radiotherapy | 34.2 Gy in 19 fractions of 1.8 Gy each |
| Stereotactic Body Radiotherapy | 19 Gy in 2 fractions of 9.5 Gy each |
| Permanent Prostate Seed Implant (PPI) | 
 • 108 Gy for I-125 • 90 Gy for Pd-103 |
| HDR brachytherapy | 15 Gy in one fraction |

4.2 Technical Factors

For Phase I, IMRT is necessary to achieve conformality. No specific field arrangement is required. External beam radiotherapy will be delivered with megavoltage equipment at energies ≥ 6 MV.

4.2.1 IMRT Localization, Simulation, and Immobilization

Simulation will be CT-based in all cases. A MRI is recommended to define the extent of disease and for delineation of the urethra. Rectal contrast is discouraged because it may distend the rectum and artificially displace the prostate in the anterior direction. IV contrast is permitted to assist in identifying the pelvic vessels. Patients will be positioned supine on a flat tabletop with a customized thermoplastic immobilization cast or a

molded foam cradle for stabilization and setup reproducibility. The degree of bladder fullness should be made to duplicate the degree of fullness anticipated for daily treatment, i.e., if the patient is instructed to maintain a full bladder for treatment, he should be simulated as such (especially for cases in which image guidance or adaptive treatments are not implemented). The rectum should be kept as empty as possible; consider an enema 1-2 hours prior to simulation. CT images should be acquired at a slice thickness of ≤ 3 mm from the top of the iliac crests superiorly to the perineum inferiorly. Target volumes and normal critical structures will be defined in the slices in which they are visualized.

4.2.2 Treatment Planning/Target Volumes

4.2.2.1 Target Volume for Step 1

The target volume (CTV1/PTV1) for step 1 will be the pelvic lymph node, which include the internal iliac, external iliac, obturator, and common iliac nodes, prostate, and seminal vesicles. The presacral nodes may be included if desired depending if dose constraints to the rectum are achievable. Sentinel lymph node imaging may be utilized to guide target volume delineation of CTV1. A total dose of 45 Gy in 25 fractions of 1.8 Gy each will be delivered to this volume with intensity modulated radiation therapy.

4.2.2.2 Step 1 Pelvic Lymph Node Irradiation

The Clinical Target Volume 1 (CTV1) will include the obturator, external iliac, proximal internal iliac and common iliac nodes, using the vascular structures, up to a level corresponding to the top of L4-L5. Also included will be the prostate and seminal vesicles. Please refer to the pelvic nodal atlas at the RTOG Web site (Pelvic Lymph Node Volumes for Prostate Cancer Atlas; <http://www.rtog.org/atlas/PelvicLymphNodeProstateAtlas/main.html>). The presacral nodes from L5-S1 to S3 may be included if desired depending on whether the dose constraints to the rectum are achievable (see Table 4). The CTV1 will extend superiorly from L4-L5 to 0.5 cm below the tip of the urethral contrast dye (if used) and no less than the entire prostate gland. Lateral borders will be at least 1 cm from the pelvic brim. In the lateral fields, the external and internal iliac lymph nodes below the SI joints, and the posterior extension of the seminal vesicles should be covered. The usual posterior border is approximately S2-3, but CT anatomy should take precedence. The inferior extent of the external iliac lymph nodes is at the top of the femoral heads. The inferior extent of the obturator lymph nodes is at the top of the symphysis pubis. The CTV1 will include a 7 mm margin in 3-dimensions to the contoured iliac vessels, but not extend outside of the true pelvis, into the pelvic musculature nor into adjacent identifiable organs, such as the bladder, rectum or other bowel. Extension of the CTV into adjacent bone may be carved out. In addition, sentinel lymph node imaging may be utilized to guide CTV1 target delineation.

For patients with gross nodal involvement (cN1) as determined by CT or MRI, a sequential boost to 59.4 Gy in 9 fractions of 1.8 Gy each is allowed to the involved node(s). It is critical to maintain small bowel dose constraints as listed in Table 4. If bowel dose constraints are unable to be met, the gross nodal boost dose should be reduced to 57.6 Gy or 55.8 Gy to meet the small bowel dose constraint. The final dose should be recorded if a gross nodal boost dose is utilized.

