| Duration of Therapy | Patients will receive a total duration 24 months of androgen deprivation therapy including leuprolide and enzalutamide with radiation therapy. The initial phase of radiation therapy will be delivered Monday-Friday, except for holidays, for a total of 15 treatment days. The boost phase (phase 2) of radiation therapy is one day for brachytherapy. |
| Duration of Follow up | Patients will be followed for up to 36 months after completion of radiation treatment |
| Duration of study | 60 months |
| Study Treatment | Combined androgen blockade with leuprolide and enzalutamide will be administered with whole pelvic radiotherapy to a total dose of 45 Gy followed by brachytherapy boost. |
| Safety Assessments | Safety will be assessed through a summary of adverse events evaluated by NCI CTCAE v. 4.0. |

List of Abbreviations

| | |
|--------|---|
| AE | adverse event |
| ALT | alanine aminotransferase |
| AST | aspartate aminotransferase |
| ATC | Anatomical Therapeutic Chemical (Classification System) |
| AUC | area under the curve |
| CBC | complete blood cell (count) |
| CHR | Committee on Human Research (UCSF IRB) |
| CR | complete response |
| CRC | Clinical Research Coordinator |
| CRF | case report form |
| CT | computerized tomography |
| CTCEA | Common Terminology Criteria for Adverse Events |
| CTMS | Clinical Trial Management System |
| DSMC | Data and Safety Monitoring Committee |
| DSMP | Data and Safety Monitoring Plan |
| ECOG | Eastern Cooperative Oncology Group |
| FDA | Food and Drug Administration |
| GCP | Good Clinical Practice |
| HDFCCC | Helen Diller Family Comprehensive Cancer Center |
| HGB | hemoglobin |
| ICH | International Conference on Harmonization |
| IRB | Institutional Review Board |
| IV | intravenous |
| LFT | liver function test |
| MRI | magnetic resonance imaging |
| NCI | National Cancer Institute |
| PD | disease progression |
| PR | partial response |
| PRC | Protocol Review Committee (UCSF) |
| PSA | Prostate Specific Antigen |
| QOL | Quality of Life |
| SD | stable disease |
| SD | standard deviation |
| ULN | upper limit of normal |

Table of Contents

Protocol Signature Page 2

List of Abbreviations 6

Table of Contents 7

1 Background: 10

 1.1 High-Risk Prostate Cancer 10

 1.2 Enzalutamide 10

 1.3 Rationale of the Proposed Study 11

 1.4 Rationale for Correlative Studies 11

2 Objectives of the Study 12

 2.1 Primary 12

 2.2 Secondary 12

 2.3 Correlative Studies 13

 2.4 Endpoints 13

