3.2.1 Inclusion Criteria

1. Histologically confirmed diagnosis of adenocarcinoma of the prostate within 25 weeks prior to registration at very high risk of recurrence as determined by 2 or more of the following combinations:
 - cT3a/b
 - PSA \geq 20
 - Gleason score 8-10
 - \geq 33% core involvement

OR

any patient with pelvic lymph node involvement \geq 1cm as determined by pelvic CT or MRI imaging will meet eligibility criteria for enrollment.

2. Standard staging exams for patients with high-risk prostate cancer including bone scan or NaF PET/CT scan, and pelvic and prostate MRI.
3. No distant metastases (M0) on bone scan or NaF PET/CT within 14 weeks prior to registration. Equivocal bone scan findings are allowed if the physician determines that distant metastases are unlikely based on clinical judgment.
4. Zubrod Performance Status 0-2 within 14 weeks prior to enrollment.
5. Age ≥ 18
6. CBC with differential obtained within 14 weeks prior to registration on study, with adequate bone marrow function defined as follows:
 - a. Absolute neutrophil count (ANC) $\geq 1,800$ cells/mm³
 - b. Platelets $\geq 100,000$ cells/mm³
 - c. Hemoglobin ≥ 8.0 g/dl (The use of transfusion or other intervention to achieve Hgb ≥ 8.0 g/dl is acceptable)
 - d. Serum creatinine < 2.0 mg/dl and creatinine clearance > 40 mL/min
 - e. Bilirubin $< 1.5 \times$ ULN
 - f. ALT or AST $< 2 \times$ ULN
7. Patients, even if surgically sterilized (i.e., status post vasectomy), who:
 - a. Agree to practice effective barrier contraception during the entire study treatment period and for 4 months (120 days) after the last dose of study drug, or
 - b. Agree to completely abstain from intercourse
8. Patient must be able to provide study-specific informed consent prior to study entry.

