4.3 Dose Specification/Technical Considerations: IMRT

Table 4: Dose Specifications/Technical Considerations IMRT

| Normal Organ | No More than 15% volume receives dose that exceeds | No more than 25% volume receives dose that exceeds | No more than 35% volume receives dose that exceeds | No more than 50% volume receives dose that exceeds |
|--------------|--|--|--|--|
| Bladder | 80 Gy | 75 Gy | 70 Gy | 65 Gy |
| Rectum | 75 Gy | 70 Gy | 65 Gy | 60 Gy |
| Bowel | Max point dose 0.03 cc <56 Gy, 1 cc <54 Gy | | | |
| Penile Bulb | Mean dose less than or equal to 52.5 Gy | | | |

While every effort should be made to deliver prescription doses to the PTV as specified while adhering to these constraints, it is recognized that certain anatomical factors may prevent this. A prescription dose reduction to a level of 77.4 Gy or 75.6 Gy is permitted

if constraints cannot be met at a prescription dose of 79.2 Gy. For purposes of compliance, up to a 5% absolute increase in the volume of critical structure receiving greater than the specified dose will be considered “variation acceptable,” e.g. up to 20% of the rectum may receive a dose of >75.6 Gy without a protocol deviation. Any increase in critical structure volume greater than 5% receiving more than the specified dose will

be considered a “deviation unacceptable.” It is at this point that a dose reduction to 77.4 Gy or 75.6 Gy should be implemented. The prescription dose should be the maximum deliverable up to 79.2 Gy while respecting the critical normal structure constraints. Of note, the penile bulb constraint is to be regarded as a guideline, and adherence to this should not, in any way, result in a reduction of the prescription dose or compromised dose coverage of the target volume.

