- The CTV is the prostate gland and the seminal vesicles.
- Critical structures to be defined using CT planning include the bladder, rectum, urethra, and penile bulb within the volume of interest. The outermost extent of the bladder/rectal wall will define those structures. The urethra is defined by the outer surface of the Foley catheter.
 - The volume of bladder and rectum receiving 75% of the prescription dose must be kept to less than 1 cc ($V_{75} < 1$ cc) and the volume of urethra receiving 125% of the prescription dose must be kept to less than 1 cc ($V_{125} < 1$ cc) and urethral V_{150} should be 0%. If the dose to normal critical structures cannot be kept below the specified level, we recommend readjusting the implant or repeating the implant procedure until a more optimal implant is obtained.
 - Compliance Criteria: A prescription dose of 15 Gy in one fraction will be delivered to the PTV1. Ninety percent coverage of the PTV with the prescription dose is considered per protocol, $\geq 85\%$ but $< 90\%$ is considered variation acceptable, and $< 85\%$ coverage is considered deviation unacceptable.
 - Catheter Position Verification: Visual inspection of the catheters prior to delivery of each treatment is required. Fluoroscopy or CT may be also used to verify the position of the catheters in relation to the Foley catheter balloon and fiducial markers. The physician may adjust the catheters if catheter displacement is identified prior to the treatment. If the catheters cannot be satisfactorily repositioned and the PTV and normal critical structure DVH parameters are not met with a new plan, then the treatment should be postponed until a satisfactory implant is done. If the planning process is repeated, then a second set of data should be submitted.
 - Catheter Removal: After completion of the treatment all catheters will be removed.

5 Drug Therapy

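### Nodal boost prescription for cN1 patients: nine sequential 1.8 Gy fractions after 45 Gy give 61.2 Gy, not the stated 59.4 Gy, which needs eight

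*Combined protocol and SAP*

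**What the plan says.** Section 4.2.2.1 defines the step 1 volume as the pelvic nodes, prostate and seminal vesicles, and prescribes: "A total dose of 45 Gy in 25 fractions of 1.8 Gy each will be delivered to this volume".

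Section 4.2.2.2 adds an option for gross nodal involvement (cN1) on CT or MRI: "a sequential boost to 59.4 Gy in 9 fractions of 1.8 Gy each is allowed to the involved node(s". If the bowel limits cannot be met, "the gross nodal boost dose should be reduced to 57.6 Gy or 55.8 Gy to meet the small bowel dose constraint". It also asks that "The final dose should be recorded if a gross nodal boost dose is utilized".

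The bowel limits are in Table 4 (Section 4.3): "Max point dose 0.03 cc <56 Gy, 1 cc <54 Gy".

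Node-positive patients are a named entry group. Under Section 3.2.1, pelvic nodal involvement of at least 1 cm "as determined by pelvic CT or MRI imaging will meet eligibility criteria for enrollment", without any of the other high-risk features.

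**The concern.** A sequential boost *to* a dose is a cumulative prescription, so the boost fractions must make up the difference between 45 Gy and the stated total. Nine fractions of 1.8 Gy overshoot that difference by one fraction. No other section gives the number of boost fractions, and nothing says whether the total or the count takes precedence.

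This is an operative prescription, not background text. A planner who follows the count delivers one more fraction than a planner who follows the total, and each can point to the protocol. The compliance bands cover the 45 Gy PTV (Table 1), the critical structures (Section 4.3), LDR (Section 4.5) and HDR (Section 4.6). None covers the nodal boost total, so there is no rule for classifying a delivered 61.2 Gy.

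Bowel dose is the limiting factor that the plan itself names for this boost. Toxicity is also a primary endpoint (Section 2.4.1) and drives the termination rule (Sections 3.4 and 9.3). The nodal dose should therefore mean the same thing for every boosted patient, particularly as the protocol provides for participating sites.

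**Working it through.** **Inputs**

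- Base dose to the nodes: 45 Gy in 25 fractions of 1.8 Gy (Section 4.2.2.1).
- Boost: to 59.4 Gy, 9 fractions, 1.8 Gy each (Section 4.2.2.2).
- Fallback totals: 57.6 and 55.8 Gy (Section 4.2.2.2).
- Bowel limits: 0.03 cc below 56 Gy, 1 cc below 54 Gy (Table 4).

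**Check that the plan's other dose sums reproduce**

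- Step 1: 25 × 1.8 = 45.0 Gy, as stated.
- Step 2 IMRT (Section 4.2.3): 19 × 1.8 = 34.2 Gy, as stated.
- Prostate total (Section 4.3): 45 + 34.2 = 79.2 Gy, as stated.

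**The nodal boost**

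Cumulative dose = 45 + (fractions × 1.8).

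| Boost fractions | Added dose (Gy) | Cumulative dose (Gy) | In the plan? |
|---|---|---|---|
| 6 | 10.8 | 55.8 | second fallback |
| 7 | 12.6 | 57.6 | first fallback |
| 8 | 14.4 | 59.4 | stated total |
| 9 | 16.2 | 61.2 | stated fraction count |

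Fractions needed for the stated total: (59.4 − 45) / 1.8 = 14.4 / 1.8 = 8.

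**Other readings tried**

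- Nine fractions from 45 to 59.4 Gy would be 14.4 / 9 = 1.6 Gy each, not 1.8.
- Treating 59.4 Gy as the boost alone gives 59.4 / 9 = 6.6 Gy per fraction.
- For nine fractions of 1.8 Gy to end at 59.4 Gy, the base would have to be 59.4 − 16.2 = 43.2 Gy (24 fractions), which the plan does not use.

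None fits all the stated figures.

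**Which number is likely wrong**

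The totals 59.4, 57.6 and 55.8 Gy fall in steps of 1.8 Gy and correspond to eight, seven and six fractions. Section 4.3 uses the same pattern for the prostate: 79.2 Gy, reducible to 77.4 or 75.6 Gy, again two steps of one fraction. Had 61.2 Gy been the intended top dose, the first reduction would be expected at 59.4 Gy.

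**Size**

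- Difference: 61.2 − 59.4 = 1.8 Gy; 1.8 / 59.4 = 3.0%.
- Where bowel lies next to a boosted node, the share of the prescribed total to which dose must fall at the bowel limit is:

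| Limit | At 59.4 Gy | At 61.2 Gy |
|---|---|---|
| 0.03 cc below 56 Gy | 56 / 59.4 = 94.3% | 56 / 61.2 = 91.5% |
| 1 cc below 54 Gy | 54 / 59.4 = 90.9% | 54 / 61.2 = 88.2% |

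**The case against.** The best reply is that the text nearly corrects itself. The dose is given as a cumulative total, the fallbacks step down from 59.4 Gy, and it is the final dose that must be recorded. A careful planner would probably take 59.4 Gy as governing and read the nine as a wrong digit. The boost is also optional and limited to cN1 patients. Harm requires someone to follow the count over the total, and the excess is then one fraction. The Table 4 bowel limits bind under either reading, with an instruction to reduce the dose if they cannot be met. The fall-off percentages matter only where bowel is close to the node, and the documents give no such geometry.

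Most of this stands, and it limits the importance of the point. No excess bowel dose has been shown, nor any effect on an endpoint. That eight fractions was intended is an inference; the documents do not say so. What the reply does not remove is the inconsistency. The fraction count and size are instructions in their own right, and the plan does not say that the total overrides them.

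**Conclusion.** The concern holds. With the 45 Gy base from Section 4.2.2.1, the boost as written in Section 4.2.2.2 is arithmetically impossible: nine fractions of 1.8 Gy reach 61.2 Gy, and 59.4 Gy takes eight. The inconsistency itself is certain. That the nine should be an eight is likely, given the dose ladder, but needs clinical confirmation.

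The effect is at most one extra 1.8 Gy fraction (3.0% of the nodal total) in cN1 patients who receive the optional boost. The documents do not give their expected number. The PSA-CR comparison, its sample size and its power do not depend on this figure. It should be fixed because a prescription sentence should not carry incompatible numbers, not because patient harm has been demonstrated.

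**What to change.** 1. Have the radiation oncology leads confirm the intended nodal total.
2. If it is 59.4 Gy, amend Section 4.2.2.2 to read 59.4 Gy (14.4 Gy in 8 fractions of 1.8 Gy), with fallbacks of 57.6 Gy (7 fractions) and 55.8 Gy (6 fractions).
3. Tell sites, once confirmed, that the cumulative total governs.
4. Check the recorded nodal doses of patients already boosted, and note any who received 61.2 Gy.

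Two minor labels can be corrected in the same amendment. Neither bears on the conclusion above, because other sections already resolve both.

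- The synopsis (Duration of Therapy) gives the initial radiation phase "for a total of 15 treatment days", where Section 4.2.2.1 gives 25 fractions. Change 15 to 25.
- The HDR compliance criterion in Section 4.6 says "A prescription dose of 15 Gy in one fraction will be delivered to the PTV1", where Section 4.2.3 assigns the step 2 boost to PTV2. Change PTV1 to PTV2.

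The cost is one clarifying amendment or site memo, plus a check of doses the protocol already requires to be recorded. It adds no procedures and no patients.
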